## 5. Specific Aims:

The specific aims of our pilot study are to: 1) test the feasibility of a genotype-guided opioid prescribing approach for patients undergoing an outpatient surgical procedure, a group at high risk for persistent opioid use; and 2) evaluate the effect of genotype-guided post-surgical pain management on pain control and opioid prescribing. This will be a randomized, open-labeled pilot pragmatic clinical trial. A total of 320 patients will be recruited from the UF Health Gainesville and the Villages Orthopedic Clinics during their Initial Evaluation for total joint (hip or knee) replacement once the decision for surgery is made. For patients randomized to the genotype-guided arm, a saliva or buccal cell sample will be collected unless venipuncture is done for other reasons and then a blood sample will be collected for genotyping. Genotyping will be performed in the UF Health Pathology Laboratory and results placed in the electronic health record (EHR). For patients in the usual care arm, a genetic sample will be collected for clinical genotyping at the end of the study. At baseline (within 30 days of surgery) and 2 weeks  $\pm$  4 days after surgery, all patients will be asked to complete the PROMIS measures for assessment of pain intensity, physical functioning, emotional functioning, mobility, and a measure of medication misuse. We will also assess utilization of pain medications during the 2 weeks  $\pm$  4 days following surgery. We hypothesize that CYP2D6-guided post-operative pain management is feasible, with reduced use of codeine, tramadol, hydrocodone, and oxycodone in patients with the PM, IM, or UM phenotype, and will improve pain control in PMs and IMs and reduce use of more addictive opioids (i.e. DEA schedule II opioids) in patients with the NM phenotype.

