For patients in the genotype arm, *CYP2D6* genotyping will be done in the CAP/CLIA-licensed UF Health Pathology Laboratory at Rocky Point with results reported in the EHR. It is expected that results will be reported prior to surgery in the absence of any genotyping error. Patients will be categorized as *CYP2D6* PM, IM, NM, or UM based on *CYP2D6* genotype/activity score and FDA guidance on drug interactions. Strong inhibitors (e.g. bupropion, fluoxetine, paroxetine) phenoconvert patients to PMs, with moderate inhibitors (e.g. duloxetine, fluvoxamine) reducing *CYP2D6* activity scores by 50%. Using a standardized consult note, as we are using for an on-going study in cancer pain patients (NCT02664350), recommendations will be made to avoid tramadol, hydrocodone, codeine, and oxycodone in PMs, IMs, and UMs and to use an alternative opioid (e.g. morphine, hydromorphone) or non-opioid (e.g. NSAID). Consideration of tramadol as the first line opioid will be recommended for NMs. Patients randomized to usual care will have their DNA sample collected at the Initial Evaluation visit and stored until they have completed the 2 week follow-up, at which time, the sample will be genotyped with the result reported in the EHR. This approach was successfully used in our previous study in chronic pain. Genotyping will be funded by the grant. Patients will be compensated in the amount of \$25 gift certificate for their participation. Study participation will be terminated for any patient

randomized into the usual care arm who gets genotyping done for clinical care before study completion. These patients will receive \$10 compensation for study participation.

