Patients in both arms will be asked to complete surveys for PROs at the Pre-Operative visit (within 1 month of surgery) or via phone call within 30 days prior to surgery. Patients will be asked the PROMIS Pain intensity survey and about opioid consumption at 48 hours  $\pm$  24 hours and again at 1 week  $\pm$  4 days post-surgery. At 2 weeks  $\pm$  4 days post-surgery, utilizing the PROMIS measures developed with the NIH Common Fund ([www.nihpromis.org](http://www.nihpromis.org)). Surveys will be completed with the study coordinator in clinic or by telephone after their clinic visit, or if patients prefer, electronically through a link sent to them to be completed prior to their surgical procedure. Outcome measures for the proposed study were selected based on guidance in the Initiative on Methods, Measurement, and Pain Assessment in Clinical Trials (IMMPACT), which recommends that pain outcome studies assess the domains of pain, physical functioning, and emotional functioning. The specific PROs we will assess are shown in **Table 1**. These measures are well adapted for use in the clinical setting, and employ a Computer Adaptive Test (CAT) approach that minimizes respondent burden by reducing the number of questions needed to arrive at a valid PRO. We have significant experience administering the PROMIS measures to assess pain intensity using an IPAD tool from our recently completed study in patients with chronic pain. We will also assess how well patients are able to do their usual activities with the HOOS or KOOS survey.

Data will be recorded directly into the REDCap server. Patients desiring survey completion on a personal electronic device will receive a link by Short Message Service (SMS) to their cell phone using TWILIO through REDCap or email. For collection of data in those not completing surveys on personal electronic devices, or not completing them within specified time windows, we will use a call center approach to data collection. The UF Center for Quality Medication Management (CCQM) provides medication therapy management in a call-center model, with vast experience scripting for consistent data collection, and speaking to patients about drug therapy and therapy-related outcomes. Pharmacy technicians in the CCQM will be given a telephone script to use for calling study participants for survey completion.

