**Data collection.** In addition to data from the PROMIS measures, we will collect the following patient information from the EHR: name, medical record number, demographics (age, sex, race, ethnicity), past medical history, social history (smoking status), surgical procedure scheduled, medications (chronic, pre-operative, post-operative, and discharge medications), use of regional anesthesia or nerve block, hospital length of stay, use of opioids at 3 and 6 months (to assess persistent opioid use). In addition, opioid consumption will be assessed at the 2 week ( $\pm$  4 day) data collection point via patient interview.

**Outcomes.** The primary outcomes are feasibility of the clinical implementation (Table 2) and opioid utilization. The secondary outcomes will be pain intensity, physical functioning, emotional functioning, and mobility at 2 weeks  $\pm$  4 days post operatively.

Table 1. PROMIS Measures to be employed	
Scales	Subscales
Pain Intensity	Worst and average pain intensity in last 7 days and current pain
PROMIS 43 (7 subscales + 1 pain intensity question)	Physical functioning: 

• Pain interference

• Physical function

• Sleep disturbance

• Social role & activities functioning

 Emotional functioning: 

• Fatigue

• Anxiety

• Depression

Others	

• Prescription pain medication misuse

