**Data analysis.** For the primary analysis, we will collect data on the implementation success metrics in **Table 2**. For opioid utilization measures (morphine equivalent dose (MED), schedule IV/II opioid use), we will determine the proportion of patients prescribed specific opioids and self-reported opioid use, since patients may not take any or all of the opioid prescribed. Opioid use (proportion) will be compared between arms by  $\chi^2$  analysis or Fisher's exact test. For our secondary outcome of pain intensity, we will create a composite score of current pain and worst and average pain in last 7 days from the pain intensity subscales. We will use pain intensity at 14 days post-surgery (with a  $\pm 4$  days data capture window). Comparisons between the genotype-guided and usual care groups will be by analysis of covariance (ANOVA), adjusting for baseline pain scores and other baseline differences between the two groups and accounting for MED and/or use of opioids other than tramadol, codeine, hydrocodone, or oxycodone. While beyond the scope of this pilot, we also plan to collect data on prevalence of new persistent opioid use at 6 months (in those who were opioid naive in the year prior to the study) and differences between groups in the PRO of prescription pain medication misuse.

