**Table 2. Clinical Implementation Success metrics**

- % of patients agreeing to participate
- % of patients in genotype arm with a genotype leading to a clinical recommendation for alternative therapy
- % of patients in whom a genetic-guided recommendation is accepted by the clinician
- If recommendation is not accepted, what are the prevailing reasons
- Patient reported opioid use by CYP2D6 phenotype

**Power analysis.** We acknowledge that the proposed trial will have insufficient power to examine PROs (e.g. pain intensity). However, these data will be collected to provide preliminary data on the effects of genotype-guided therapy on PROs to inform a future larger pragmatic clinical trial, and also to document that there are not obvious trends of the genotype-guided approach leading to worse pain control, which in turn could lead to worse post-surgical outcomes. Moreover, if we assume that 25% of patients in the implementation arm will be a PM, IM, or UM (based on genotype and drug interactions) and that codeine, tramadol, hydrocodone, and oxycodone will be avoided in these patients, whereas the remaining 75% of patients in the implementation arm will be prescribed tramadol and nearly all (i.e. 95%) of controls will be prescribed tramadol, codeine, hydrocodone, or oxycodone we will have  $>80\%$  power, with an alpha of 0.05, to detect a difference in use of codeine, tramadol, hydrocodone, or oxycodone between arms.

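### The only specified between-arm pain model adjusts for opioid dose and opioid type, which the intervention is meant to change, so its arm coefficient is not the effect of genotype-guided management on pain

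*Combined protocol and SAP*

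**What the plan says.** - **Aim.** The second aim in section 5 is to "evaluate the effect of genotype-guided post-surgical pain management on pain control and opioid prescribing".
- **Intervention.** For the genotype arm, section 6 says that "recommendations will be made to avoid tramadol, hydrocodone, codeine, and oxycodone in PMs, IMs, and UMs and to use an alternative opioid" or a non-opioid. Normal metabolisers are steered towards tramadol as first-line opioid.
- **Timing.** Randomisation follows consent, before surgery. Opioid use is measured afterwards: "Patients will be asked the PROMIS Pain intensity survey and about opioid consumption at 48 hours" and again at 1 week, and "opioid consumption will be assessed at the 2 week" point as well.
- **Outcomes.** "The primary outcomes are feasibility of the clinical implementation (Table 2) and opioid utilization". The Data analysis paragraph lists the "opioid utilization measures (morphine equivalent dose (MED), schedule IV/II opioid use"). Pain intensity is secondary.
- **Pain model.** The day-14 pain composite is compared between arms by analysis of covariance. The model adjusts for baseline pain and other baseline imbalances, and then, as a separate item, is "accounting for MED and/or use of opioids other than tramadol, codeine, hydrocodone, or oxycodone".
- **Use of the pain data.** The Power analysis paragraph concedes too little power for patient-reported outcomes. It keeps the pain data to inform a larger trial and "also to document that there are not obvious trends of the genotype-guided approach leading to worse pain control".

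No pain model without the opioid terms is specified, and no mediation question is defined. The Abstract says only that pain scores are to be compared between groups.

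**The concern.** Randomisation makes the arms comparable at baseline. A covariate measured after randomisation and affected by the intervention undoes that protection in two ways.

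1. **It blocks the route of effect.** The trial's rationale is that genotype changes opioid choice and opioid choice changes pain. Holding opioid type and dose fixed removes the part of the effect that runs through them.
2. **It can create bias.** Patients in more pain may take more opioid. Pain sensitivity would then drive both MED and pain, and comparing arms at equal MED would compare patients who differ in pain sensitivity.

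The coefficient can be shrunk, exaggerated or given a false sign. The wording also permits three models (MED alone, other-opioid use alone, or both) with no rule for choosing among them in an open-label trial.

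Both stated uses of the pain data need the total effect by randomised arm. If guided patients hurt more and took more opioid, the MED term would hide part of the trend the plan wants to see. If they took less opioid with equal pain, it could make the guided arm look worse.

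**Working it through.** **The plan's own power figure.** The only one concerns opioid use: 95% of controls v 75% of the guided arm on a listed opioid, alpha 0.05 (two-sided assumed), power above 80%. With 320 patients at 2:1 (213 v 107), the two-proportion formula gives 99.9%. The figure stands, and the pain model does not touch it.

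**Are the terms post-randomisation?** Yes. The sentence lists them apart from the baseline terms, MED is classed as a utilization measure, consumption is asked after surgery, and chronic opioid users are excluded. The power assumptions imply up to 25% of the guided arm but at most 5% of usual care on an opioid outside the four listed drugs, so that covariate differs between arms by design. The contrast is an upper bound, because some of these patients would get a non-opioid.

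**Size of the distortion from MED alone.** The documents give no SD, correlation or MED difference for this trial, so these inputs are assumed:
- pain residual SD given baseline = 1, within-arm MED SD = 1, no attrition
- r = within-arm correlation of MED with pain given baseline
- d = guided minus usual-care difference in mean MED, in SD units
- higher score = worse pain

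Formulas:
- Adjusted arm effect = true total effect − r × d
- SE, baseline-only model = √(1/213 + 1/107) = 0.118
- SE with MED added = 0.118 × √(1 − r²) × √(1 + d² × 0.223), where 0.223 = (213/320) × (107/320)

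Worked case, no true effect, r = 0.4, d = −0.3: adjusted effect = 0 − 0.4 × (−0.3) = +0.12. SE = 0.118 × 0.917 × 1.010 = 0.110. Ratio 1.09, so the two-sided 5% test rejects 19% of the time.

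| True effect | r | d | Effect shown with MED added | Rejection |
|---|---|---|---|---|
| 0 | any | 0 | 0 | 5% |
| 0 | 0.2 | −0.3 | +0.06 | 8% |
| 0 | 0.2 | −0.5 | +0.10 | 13% |
| 0 | 0.4 | −0.3 | +0.12 | 19% |
| 0 | 0.4 | −0.5 | +0.20 | 43% |
| +0.30 | 0.4 | +0.3 | +0.18 | 37% |
| +0.30 | 0.4 | +0.5 | +0.10 | 15% |

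The bias changes sign with d. Baseline-only analysis keeps 5% rejection under no effect. For a true worsening of +0.30 it shows +0.30 with 72% power (0.30/0.118 = 2.53). Simulation at 3,000 replicates per cell agrees to within about two percentage points.

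**Other-opioid use alone.** Assume 25% v 5% use, no true effect, and users differing from non-users within arm by ±0.5 SD in pain. Bias = −(±0.5) × (0.25 − 0.05) = ∓0.10 SD, with rejection of about 13%. In a different case, let all the benefit come through switching, at 1.0 unit per switcher. The total effect is then −1.0 × 0.20 = −0.20, and a large-sample simulation returns 0.00 once this term is added.

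**The three permitted models.** Take an arbitrary true effect of −0.11 SD, r = 0.4, d = −0.3, and other-opioid use unrelated to pain. Baseline-only gives −0.11 and other-opioid alone −0.11. MED alone gives −0.11 + 0.12 = +0.01, and both terms together also give +0.01. With d = +0.3, MED alone gives −0.11 − 0.12 = −0.23. The choice of model can decide whether a benefit appears at all.

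**The case against.** The strongest objection concerns consequence. Pain is a secondary outcome in a pilot that admits it cannot test patient-reported outcomes. The primary comparison, sample size and stated power are untouched. At r = 0.2 the bias is 0.06 to 0.10 SD, below one standard error of the arm difference (0.118 SD), and at r = 0.4 with d = −0.3 it is about one standard error. This stands and limits the weight of the point. But low power makes an estimate imprecise, whereas this makes it an estimate of something else, which more patients would not cure.

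Second, every magnitude is assumed. If only the 25% with an actionable phenotype changed their MED, a whole-arm d of 0.5 would need a shift of 0.5/0.25 = 2 SD in them. That is fair, although normal metabolisers are also steered, so a whole-arm shift is possible. The figures also say nothing specific about poor and intermediate metabolisers, to whom the pain hypothesis refers.

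Third, the Abstract's general statement does not exclude plain arm summaries, and the check for worse pain is not expressly tied to the covariance model. This softens the point. But the Data analysis paragraph is the only place that specifies a method.

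Finally, pain at a given level of opioid use is a reasonable supplementary question. It is, and the fix keeps that model under its proper label.

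**Conclusion.** The concern holds: the pain model is wrong as written for the stated aim. Its arm coefficient is at best a direct effect at fixed opioid dose and type, and it is biased even for that if pain sensitivity drives both opioid use and pain. The two approaches agree only if the opioid terms neither carry the effect nor share causes with pain (or, for MED, if the arms do not differ on it), which runs against the trial's premise.

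The direction and size cannot be known in advance. Under the assumed values in the table (r of 0.2 to 0.4, MED differences of 0.3 to 0.5 SD), the distortion is 0.06 to 0.20 SD and false-positive rates are 8% to 43%. This should be fixed, but it is confined to the preliminary pain estimate and the check for worse pain control.

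**What to change.** Replace the sentence describing the pain comparison in section 6 (Data analysis) with:

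*Pain intensity in the two arms will be compared as randomised by analysis of covariance, adjusting for baseline pain score and prespecified baseline covariates only (for example hip or knee procedure). MED and opioid type will be reported by arm beside pain, as outcomes. Any model that also includes MED or opioid type is exploratory or a mediation analysis, will be labelled as such, and does not estimate the effect of genotype-guided management on pain.*

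The essential change is to take the opioid terms out of the main model. Naming the baseline covariates in advance is a useful addition that the correction does not depend on. If the opioid-adjusted model is kept as exploratory, the plan should say which of the three versions is meant.

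The cost is one sentence. Baseline pain and the scheduled procedure are already collected, and no new data, patients or change to the power statement are needed.

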**Table 2. Clinical Implementation Success metrics**

- % of patients agreeing to participate
- % of patients in genotype arm with a genotype leading to a clinical recommendation for alternative therapy
- % of patients in whom a genetic-guided recommendation is accepted by the clinician
- If recommendation is not accepted, what are the prevailing reasons
- Patient reported opioid use by CYP2D6 phenotype

**Power analysis.** We acknowledge that the proposed trial will have insufficient power to examine PROs (e.g. pain intensity). However, these data will be collected to provide preliminary data on the effects of genotype-guided therapy on PROs to inform a future larger pragmatic clinical trial, and also to document that there are not obvious trends of the genotype-guided approach leading to worse pain control, which in turn could lead to worse post-surgical outcomes. Moreover, if we assume that 25% of patients in the implementation arm will be a PM, IM, or UM (based on genotype and drug interactions) and that codeine, tramadol, hydrocodone, and oxycodone will be avoided in these patients, whereas the remaining 75% of patients in the implementation arm will be prescribed tramadol and nearly all (i.e. 95%) of controls will be prescribed tramadol, codeine, hydrocodone, or oxycodone we will have  $>80\%$  power, with an alpha of 0.05, to detect a difference in use of codeine, tramadol, hydrocodone, or oxycodone between arms.

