**3. Abstract:**

More Americans suffer from pain than are affected by heart disease, cancer and lung disease. Opioids represent the cornerstone of pain management, yet analgesic responses to opioids are widely variable. Opioid prescriptions have tripled since 1999, paralleled by increases in opioid-related hospitalizations and deaths, contributing to the opioid epidemic. Approximately 35% of all opioid prescriptions originate from surgeons. Hydrocodone, tramadol, and codeine are among the most commonly prescribed opioids, and the cytochrome P450 enzyme, CYP2D6, is central to generation of highly potent metabolites for these opioids. CYP2D6 genotype leads to absent, reduced, normal, or increased function, conferring poor (PM), intermediate (IM), normal (NM) and ultrarapid (UM) metabolism phenotypes, respectively. Data suggest avoiding hydrocodone, tramadol, codeine, and oxycodone in PMs, IMs and UMs because of increased risk for poor response (IM and PM) or toxicity (UM). Leveraging our experience from a recent study, we will test the ***hypotheses that CYP2D6 genotype-guided management of post-surgical pain 1) is feasible, with reduced use of codeine, tramadol, hydrocodone, and oxycodone in PMs/IMs/UMs and 2) will improve post-operative pain control in PMs/IMs***

**and reduce DEA Schedule II (C-II) opioids in NMs.** Patients scheduled to undergo arthroplasty surgery will be recruited from the UF Health Gainesville and the Villages Orthopedic clinics. Patients will be randomized 2:1 to a genotype-guided versus usual care approach. For patients with CYP2D6 PM, IM or UM phenotype based on genotype or drug interactions, a recommendation to avoid hydrocodone, tramadol, codeine, and oxycodone will be made. In others, tramadol will be recommended, given evidence of its lower potential addiction risk than C-II opioids. Patient Reported Outcomes Measurement Information System (PROMIS) measures will be administered at baseline (within 30 days of surgery) and 2 weeks  $\pm$  4 days post-surgery for patients in each arm. Pain scores and assessments of physical functioning, emotional functioning, and mobility from the PROMIS measures and utilization of pain medications during the 2 week period following surgery will be compared between groups.

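### The plan would document no obvious trend to worse pain from data it calls underpowered, without defining a trend; seeing none would not show that pain is no worse

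*Combined protocol and SAP*

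**What the plan says.** Everything at issue sits in the Power analysis paragraph of section 6 (Research Plan). It opens with an admission: "We acknowledge that the proposed trial will have insufficient power to examine PROs (e.g. pain intensity"). It then gives the pain data two uses. One is preliminary data for a later, larger trial. The other is "to document that there are not obvious trends of the genotype-guided approach leading to worse pain control", because worse control could in turn harm recovery from surgery. The power figure in that paragraph, above 80%, belongs to a different outcome: it is power "to detect a difference in use of codeine, tramadol, hydrocodone, or oxycodone between arms".

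The Data analysis paragraph makes 14-day composite pain intensity a secondary outcome. It is compared by analysis of covariance, adjusting for baseline pain and other baseline differences and also accounting for morphine equivalent dose (MED) and/or use of opioids outside the four named drugs. No confidence interval, margin or decision rule is given for pain. Section 6 also collects pain at 48 hours and 1 week but describes no analysis of it. The Data Safety Monitoring Plan covers adverse events and sets no pain criterion.

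**The concern.** Admitting low power is not a fault in a pilot. The difficulty is the next step, where the same data are assigned to a statement about absence of harm by a criterion that is not defined. An imprecise comparison can show no visible or significant trend while the truth is a worsening that matters. The plan sets no rule that would separate a reassuring result from an uninformative one.

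The group in which this matters most is the normal metabolizers (NMs), whom the Power analysis paragraph takes to be about three quarters of the guided arm. For them section 6 says "Consideration of tramadol as the first line opioid will be recommended for NMs". The hypotheses in sections 3 and 5 expect better pain control only in poor and intermediate metabolizers (PMs and IMs); for NMs they expect less use of schedule II opioids. The largest group therefore has neither a pain hypothesis nor a pain check of its own.

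The planned model adds to the problem. MED and opioid type arise after randomisation and are what the intervention sets out to change, so conditioning on them can absorb part of a true worsening. At stake is whether the trial report may say that pain was no worse.

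**Working it through.** **Inputs**

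- Size and allocation: "A total of 320 patients will be recruited from the UF Health Gainesville and the Villages Orthopedic Clinics" (section 5) and "Patients will be randomized 2:1 to a genotype-guided versus usual care approach" (section 3), so 213 guided and 107 usual care.
- Significance level: "with an alpha of 0.05" (Power analysis). Sidedness is not stated; two-sided is assumed.
- Phenotype split, 25% and 75% (Power analysis), assumed equal in both arms. NMs: 75% of 320 = 240, or 160 v 80. PMs, IMs and ultrarapid metabolizers (UMs): 80, or 53 v 27. Section 4 puts UMs at 1-2%, or 3 to 6 of 320, which leaves roughly 75 PMs and IMs, or 50 v 25.
- The documents give no SD, effect size or dropout rate for pain. Results are in SD units, unadjusted, with full data. The value 0.3 SD is illustrative.

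**1. The plan's own figure.** The plan assumes "nearly all (i.e. 95%) of controls will be prescribed tramadol, codeine, hydrocodone, or oxycodone", against 75% in the guided arm.

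- Pooled proportion = (107 × 0.95 + 213 × 0.75)/320 = 0.817.
- SE under no difference = √[0.817 × 0.183 × (1/107 + 1/213)] = 0.0458.
- SE under the alternative = √(0.95 × 0.05/107 + 0.75 × 0.25/213) = 0.0364.
- Power = Φ[(0.20 − 1.96 × 0.0458)/0.0364] = Φ(3.03) = 99.9%.

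The claim of more than 80% holds, but it concerns opioid use and says nothing about pain.

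**2. Precision and miss rates for pain.**

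- SE = √(1/n₁ + 1/n₂), and the 95% CI half-width is 1.96 × SE.
- Reading A, a two-sided 5% test: the chance of non-significance at a true worsening d is about 1 − Φ(d/SE − 1.96). The table uses the non-central t, with power 0.714, 0.588 and 0.226.
- Reading B, the direction of the estimate: the chance that it shows no worsening is Φ(−d/SE).

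| Group | n | SE | CI half-width | Missed at 0.3 SD, reading A | Missed at 0.3 SD, reading B |
|---|---|---|---|---|---|
| All | 213 v 107 | 0.1185 | 0.23 | 29% | 0.6% |
| NM | 160 v 80 | 0.137 | 0.27 | 41% | 1.4% |
| PM/IM | 50 v 25 | 0.245 | 0.48 | 77% | 11% |

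Overall under reading A, for example: 0.3/0.1185 = 2.53, and 1 − Φ(2.53 − 1.96) = 28% by the normal approximation. Under reading B, Φ(−2.53) = 0.6%. If an estimate of up to 0.1 SD worse also counted as no trend, the figures would be Φ[(0.1 − 0.3)/SE] = 5%, 7% and 21%.

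**3. Sensitivity, reading A, all patients.**

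- True worsening of 0.2 SD: missed 61% of the time. At 0.4 SD: missed 8%, so detected 92%.
- Assumed 20% loss (170 v 86), at 0.3 SD: missed 38%.
- Assumed correlation of 0.3 to 0.5 between baseline and 14-day pain, at 0.3 SD: SE shrinks by √(1 − r²), and the miss rate is about 24% to 17%.
- Worsening of 0.3 SD confined to NMs: the pooled effect is 0.75 × 0.3 = 0.225 SD, missed 1 − Φ(0.225/0.1185 − 1.96) = 52% of the time.

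**4. What a confidence interval could support.** With no true difference, the chance that the upper limit falls below a margin m is Φ(m/SE − 1.96). The margins are illustrative; the documents give none.

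| Margin | All | NM |
|---|---|---|
| 0.4 SD | 92% | 83% |
| 0.3 SD | 72% | 59% |
| 0.2 SD | 39% | 31% |

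**The case against.** The strongest reply is that the plan never says non-significance is the test. A trend is more naturally read as the direction and size of the estimate, and on that reading a true 0.3 SD worsening would seldom go unseen in the whole sample. This stands. A reader might take 29%, 41% and 77% as the plan's error rates, but they apply only under the significance reading. They also ignore baseline adjustment, which would lower them, and dropout, which would raise them. A large whole-arm worsening would usually be found under either reading.

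A reader might also infer that this sentence is the trial's safeguard for patients, or that it drives the decision on a larger trial. The documents support neither. The sentence describes documentation. Adverse events are handled in the Data Safety Monitoring Plan, and acceptance of a recommendation is left to the clinician (Table 2). There is no go/no-go rule, and informing a larger trial is listed as a separate purpose.

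It can further be said that the plan claims no non-inferiority, states its low power openly, and treats pain as secondary in a pilot, so a formal margin is optional. That is fair. Reporting the estimate with its interval and drawing no inference of no harm would be enough. What the reply does not answer is that the criterion is undefined and that no visible trend, on any reading, is not evidence that pain is no worse.

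**Conclusion.** The point holds in a limited form. The plan assigns pain data that it calls underpowered to a statement about absence of worsening, leaves the criterion undefined, and gives no interval or rule elsewhere that could support the statement.

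The size depends on what the undefined term means. For a true 0.3 SD worsening, the chance of missing it runs from 0.6% to 29% overall, from 1.4% to 41% in NMs, and from 11% to 77% in PMs and IMs, between the direction reading and the significance reading. The gap therefore concerns small to moderate worsening, or worsening confined to one phenotype group. These figures assume two-sided 5%, full data, no adjustment and the plan's 25/75 split; 0.3 SD is not a value from the documents.

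It would be tempting to add that this sample can readily support a statement of no worse pain. That depends on the margin: likely at 0.4 SD, unlikely at 0.2 SD.

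**What to change.** Replace the clause on obvious trends with the following:

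> The guided-minus-usual-care difference in the 14-day pain composite, adjusted for baseline pain and not for post-randomisation MED or opioid type, will be reported with a 95% CI (expected half-width about 0.23 SD overall and 0.27 SD in NMs), overall and by CYP2D6 phenotype. Absence of an apparent or significant trend will not be reported as evidence that pain control is no worse. That statement will be made only if the CI excludes a worsening that the investigators have fixed before any comparison by arm. Otherwise the report will say that worse pain control is not excluded.

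The Data analysis paragraph needs a matching line, so that the model accounting for MED and opioid type is not the source of this estimate. The timing of the margin matters because the Data Safety Monitoring Plan has data analysed as they accrue. Investigators who prefer not to set a margin can keep the estimate, the interval and the bar on inferring no harm, and make no statement that pain is no worse.

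The cost is a few sentences and, if wanted, one clinically agreed margin. No new data are needed, since usual-care patients are genotyped after the 2-week follow-up. The downside is that the result, above all in PMs and IMs, may have to be reported as inconclusive.
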